#### **4. STUDY INTERVENTION**

Patients who are eligible to participate in the trial will be randomized (1:1 allocation) to one of two study arms, and they will take daily:

1. Low Dose Quadruple Therapy (LDQT) comprising candesartan 2 mg, amlodipine 1.25 mg, indapamide 0.625 mg, and bisoprolol 2.5 mg  
OR
2. Candesartan 8 mg

The LDQT includes quarter standard doses of four blood pressure lowering medications, which are currently approved by the US Food and Drug Administration for the treatment of hypertension. The active comparator follows current clinical practice guidelines for the majority of Americans, initiating treatment with an angiotensin II receptor blockers (ARB), which has the best side effect profile of any blood pressure lowering therapy. In both arms, if blood pressure is not controlled (SBP > 130 mmHg or DBP > 80 mmHg) at the six-week follow-up assessment, then study staff will provide participants with an open label pill of amlodipine 5 mg to supplement their study drug, which may be relevant to participants from some race/ethnic groups, including African-Americans. The combination of a calcium channel blocker with an ACE-inhibitor has been demonstrated to be more effective in reducing cardiovascular events than the combination of a thiazide-like diuretic with an ACE-inhibitor based on the ACCOMPLISH trial.

All study drugs, including LDQT, active comparator, and amlodipine add-on will be stored, controlled, and administered centrally. Control of drugs is described in full in the detailed Manual of Procedures. Drug product used in this study is subject to regulatory review and approval through an investigator-initiated investigational new drug (IND) process. Prior to use in human subjects, IND approval will be required.

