6. STATISTICAL METHODS

Descriptive statistics will summarize participant demographics and baseline clinical outcomes overall and across arms: proportion (percentages) for categorical variables; mean (\pm standard deviation) for continuous variables; and median (interquartile range) for skewed or count variables. Analyses in general will employ normal theory methods and residual diagnostics will evaluate validity of assumptions; where appropriate (i.e., in the event of low cell counts for categorical data or questions of normality), transformation of variables, nonparametric methods, or exact tests may be employed. All primary efficacy and safety analyses will be pre-specified as outlined in this SAP, and deviations from planned analyses or post hoc analyses will be labeled as such in any reports or dissemination materials.

Analyses will assume a two-sided 5% type I error rate unless otherwise specified; there will be some exploratory analyses that will involve a relaxed type I error rate (10%). There will be no corrections made for multiple hypothesis tests, as this is a phase II study evaluating preliminary efficacy.

Planned Primary, Secondary, Safety Analyses

The primary study analysis time point for all relevant outcomes is 12 weeks post randomization. The original analysis plan called for an analysis of covariance (ANCOVA), controlling for baseline value of each relevant outcome in addition to the following baseline covariates: sex, age at baseline, race/ethnicity, health literacy level (indicator of limited literacy as defined by the Newest Vital Sign instrument), and an indicator of monotherapy at baseline (vs. untreated). We deem these variables clinically relevant, important covariates; thus, all analyses will plan for adjustment for these covariates of interest (regardless of statistical significance in the current dataset) in evaluating efficacy of intervention in the present study. However, to better align with the analytic strategies of the QUARTET Australia study, and to make most efficient use of all follow-up data (both six-week and 12-week data), primary analyses will involve a linear mixed model with fixed study arm and baseline outcome value effects and a random participant effect to account for within-participant correlation. We Statistical Analysis Plan: February 9, 2022

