plan to conduct both unadjusted (for potential covariates mentioned above) and adjusted analyses. The updated details of these analyses are reserved for the statistical analysis plan. The basic analytic model will be as follows for each outcome (Y) for participant i ($i=1\dots N$) at visit j ($j=1, 2$; corresponding to Week 6 and Week 12):

$$Y_{ij} = \beta_0 + \beta_1 I(LDQT) + B_2(Y_{0i}) + B_3 visit + B_4(visit \times study\ arm) + b_i + e_{ij}$$

Under the assumption that error terms $e_{ij} \sim N(0, \sigma^2)$ is the random error term, $b_i \sim N(0, \sigma_b^2)$ is the participant-level random effect. If visit-by-study arm (B_4) is insignificant at the 5% level, we will remove that term from the model, and subsequently, we will further examine for an overall main effect for visit (B_3). If insignificant, we will also remove that effect from the model and evaluate intervention effect via the primary hypothesis test of interest:

$$H_0: \beta_1 = 0 \text{ vs. } H_1: \beta_1 \neq 0$$

for each outcome. However, if the visit-by-study arm interaction term or the visit term alone is significant, we will plan to evaluate the 12-week contrast via model-estimated least squared means as our primary analyses. All between-arm differences at both six- and 12-week time points will be reported as model-based estimates, corresponding 95% confidence limits, and p-value of the corresponding hypothesis test.

Secondary analyses (i.e., those for the secondary and exploratory outcomes of interest) will utilize data from all time points via (generalized) linear mixed modeling (GLMM) methods with the following specifications: identity, logit, or log link for continuous, binary, or count outcomes, respectively; fixed arm, visit, visit-by-arm interaction, and aforementioned covariates; and random participant effect. For secondary analyses, the model adjusted Wald type III tests for fixed effects will first evaluate significance of a visit-by-arm interaction at the 5% level of significance. If insignificant at the 5% level, then this interaction term will be removed and the model Wald type III test for fixed arm effect will evaluate the overall intervention effect in this longitudinal model at the 5% level.

The table below summarizes the general modeling strategy for each outcome. In each case, we plan to conduct both adjusted and unadjusted analyses. Adjusted analyses will include the aforementioned covariates.

Table: Modeling Strategy by Outcome

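### The random-intercept model assumes equal variance at weeks 6 and 12 although add-on starts between them, so the week-12 interval can be modestly miscalibrated when visit-by-arm is kept

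*SAP*

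**What the plan says.** SAP section 6 sets out a linear mixed model for the week-6 and week-12 values, with arm, baseline value, visit and visit-by-arm as fixed effects and "a random participant effect to account for within-participant correlation". The term b_i, normal with variance σ_b², "is the participant-level random effect"; the term e_ij, normal with variance σ², "is the random error term". Neither variance carries a visit index. Protocol 16.2 gives the same model.

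On timing, the SAP states: "The primary study analysis time point for all relevant outcomes is 12 weeks post randomization". Visit-by-arm is removed if it is not significant at 5%, and then visit likewise. If either is significant, "we will plan to evaluate the 12-week contrast via model-estimated least squared means as our primary analyses". It adds: "All between-arm differences at both six- and 12-week time points will be reported as model-based estimates, corresponding 95% confidence limits".

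Protocol section 4 sets one add-on rule, the same for the two arms. The action under it is that "study staff will provide participants with an open label pill of amlodipine 5 mg to supplement their study drug", and the condition that triggers this action is worded as follows: "if blood pressure is not controlled (SBP > 130 mmHg or DBP > 80 mmHg) at the six-week follow-up assessment".

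Neither document names another covariance structure, a robust standard error or a degrees-of-freedom method. SAP section 6 promises residual diagnostics, but the remedies it lists are transformation, nonparametric methods and exact tests.

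**The concern.** The model fixes the variance given baseline at σ_b² + σ² at both visits. The protocol changes treatment between those visits, and does so selectively: add-on goes to participants whose week-6 pressure is high. That can change the spread of the week-12 values as well as their mean. A similar benefit in everyone who steps up tends to pull high values down and shrink the spread; a benefit that varies widely between people enlarges it.

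The week-12 difference is the primary endpoint, so its interval should rest on week-12 variability. Under this model it rests partly on week-6 variability. The week-12-only ANCOVA that the mixed model replaced did not have this feature.

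**Working it through.** **1. The plan's own figures.** Inputs from SAP section 8: difference 5 mmHg, SD 15 mmHg, two-sided 5%, 80% power.
- n per arm = 2 × (1.96 + 0.842)² × 15² / 5² ≈ 141.3, or 142 with the t-test (284 in total). The planned 146 per arm gives 81.3%.
- 365 × 0.80 = 292, and 87 × 0.88 = 76.6, i.e. 77.
- Replacing SD by SD × √(1 − r²) with r = 0.5–0.6 gives 90.8–94.5% power, in line with the SAP's ANCOVA statement.

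These figures reproduce. None depends on the covariance structure, and the plan gives one SD, not one per visit. The conditional power at 87 cannot be checked because its interim inputs are not stated.

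**2. Effect of the equal-variance assumption.** Let s6 and s12 be the SDs given baseline. With complete data and visit-by-arm in the model, the week-12 standard error uses (s6² + s12²)/2 where s12² is wanted:

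SE(model) / SE(true) = √[(s6²/s12² + 1) / 2], and coverage ≈ 2Φ(1.96 × ratio) − 1.

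For s12/s6 = 0.8, the ratio is √[(1.5625 + 1)/2] = 1.13 and coverage is 97.4%. The last two columns are simulated coverage with 87 randomized and 12% missing at week 12.

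| s12/s6 | SE ratio | Coverage, formula | Simulated, random intercept | Simulated, unstructured |
|---|---|---|---|---|
| 0.8 | 1.13 | 97.4% | 97.9% | 94.6–95.1% at every ratio |
| 0.9 | 1.06 | 96.2% | 96.3% | |
| 1.0 | 1.00 | 95.0% | 95.1% | |
| 1.1 | 0.96 | 93.9% | 94.1% | |
| 1.2 | 0.92 | 92.9% | 92.3% | |

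The mean standard errors, random intercept against unstructured, were 2.58 and 2.26 mmHg at ratio 0.8, and 3.11 and 3.39 mmHg at 1.2.

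**3. What ratio could step-up produce?** The threshold rule of Protocol section 4 was applied to large simulated samples.
- From the documents: follow-up SD 15 and r = 0.55 (SAP section 8), so the SD given baseline is 15 × √(1 − 0.55²) = 12.5; baseline 141 (13) and arm difference 6.9 mmHg (Protocol section 2.3, Australian trial, the difference applied at week 6); add-on effect 6 or 9 mmHg (Protocol section 2.1, range for one standard-dose drug).
- Assumed: control week-6 mean SBP 128 or 133; control DBP 82 (SD 10), 3 mmHg lower on LDQT, correlated 0.6 with SBP; residual week-6/week-12 correlation 0.3–0.7; between-person SD of the add-on effect 0, 6 or 10 mmHg.

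| SD of add-on effect | s12/s6 | SE ratio | Coverage |
|---|---|---|---|
| 0 | 0.92–1.00 | 1.05–1.00 | 96.0–95.0% |
| 6 | 1.00–1.06 | 1.00–0.97 | 95.0–94.3% |
| 10 | 1.11–1.19 | 0.95–0.92 | 93.8–93.0% |

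Simulated trials with step-up gave a similar picture: a week-12 standard error about 7% too wide to 5% too narrow, with coverage of 93.6–96.6%. The 8% shortfall (ratio 0.92) in the table needs the 10 mmHg SD, for which the documents give no figure.

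**4. The branch without visit-by-arm.** Once that term is dropped, the arm effect is a single β₁, and the week-12 least-squares contrast equals it even if visit stays in the model. Its simulated coverage, as an interval for the average of weeks 6 and 12, was 94.6–95.3% at all ratios. In step-up simulations visit-by-arm was retained in only about 6–11% of trials.

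**The case against.** The strongest reply is that the effect is small and seldom arises. Realistic step-up shifts the standard error by a few per cent, often in the conservative direction, and under the plan's testing sequence the affected interval would usually not be the primary one. The random intercept is also a reasoned choice: the SAP wants consistency with the Australian trial and use of both visits. It promises residual diagnostics, and section 9 allows updates when assumptions fail.

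Most of this stands, and it sets the priority of the point. It does not remove it. The listed remedies do not include another covariance structure, and a structure chosen after the data are seen would be post hoc.

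Three stronger readings are tempting, and the documents do not support them.
- A reader might infer that coverage will be near 92% or 98%. SDs of 13 then 10 mmHg give a ratio of √[(1.69 + 1)/2] = 1.16 and coverage of about 97.7%; 10 then 13 give 0.89 and about 92%. Those SDs are hypothetical; no visit-specific SD is stated.
- A reader might infer that step-up must compress the week-12 values. That depends on how uniform the add-on response is.
- A reader might infer that the common baseline slope also distorts the result. In simulation step-up lowered the week-12 slope from 0.55 to about 0.41–0.48, yet with a common slope fitted coverage stayed close to 95%. Under 1:1 randomization baseline is balanced in expectation, so the arm contrast is not biased.

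**Conclusion.** The point holds as a low-priority improvement. The planned model assumes equal variance on either side of a treatment change that the protocol itself introduces. Where visit-by-arm is kept, the week-12 standard error may be about 7% too wide to 5% too narrow, with coverage of about 93–97% against a nominal 95%. The direction cannot be known in advance. The size rests on the assumed add-on response and residual correlation; errors beyond this range need visit SDs that differ by 20–30%, which the documents neither give nor exclude.

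It should not be read as a general fault in the primary interval. If visit-by-arm is dropped, the pooled interval is calibrated for the average of the two visits. Whether that average is the effect the trial wants is a separate question.

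**What to change.** For continuous outcomes, replace the random intercept in SAP section 6 (and in Protocol 16.2, so that the two agree) with an unstructured 2×2 within-participant covariance, that is, separate week-6 and week-12 variances and a free covariance. Name a small-sample degrees-of-freedom method such as Kenward–Roger, and take the week-12 contrast and its interval from that model. Both visits' data are still used. A baseline-by-visit term is not needed.

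The cost is one extra covariance parameter, a change of SAP wording, and a small departure from the random-effect model chosen for alignment with the Australian trial. The random-intercept fit can be kept as a sensitivity analysis for that comparison. The change should be made before database lock, under the version control in SAP section 9; SAP section 10 allows no final analysis before lock.

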2. STUDY OUTCOMES

In the sections below, we include the relevant specific field names for variables within the study database as of the time of SAP creation. These are indicated by the [brackets].

Primary Outcome

Primary efficacy outcome is **mean change (from baseline) in automated office systolic blood pressure (SBP) at 12 weeks** [sbpavg], and analyses will compare this change across arms for primary outcome analyses, adjusting for baseline.

Secondary Outcomes

Secondary efficacy outcomes include:

- 1) Mean automated office SBP at 12 weeks, adjusted for baseline values [sbpavg].
- 2) **Other BP measures** that will be compared across arms, controlling for baseline values:
 - a. Mean change (from baseline) in automated office SBP [sbpavg] at six weeks.
 - b. Mean automated office SBP [sbpavg] at six weeks.
 - c. Mean change (from baseline) in automated office DBP [dbpavg] at six and 12 weeks.
 - d. Mean automated office DBP [dbpavg] at six and 12 weeks.
 - e. Proportion of patients with hypertension control (SBP < 130 mmHg and DBP < 80 mmHg) at six and 12 weeks [sbpavg, dbpavg].
 - f. Proportion of patients requiring step-up treatment [amlo_dispnd].
 - g. Proportion of patients with adverse event-free hypertension control (SBP < 130 mmHg and DBP < 80 mmHg [sbpavg, dbpavg]). For the purposes of this outcome, we will define adverse event-free as absence of any events that are documented as either possibly, probably, or definitely related to study medication ([saerelate] = 3, 4, 5).
- 3) **Medication adherence:** proportion of participants deemed adherent to study medication based on the 80% criterion (i.e., participant took at least 80% of assigned study medication). This information will be captured via:
 - a. Objective pill counts [capsret6, lost6, capsret12, lost12], and
 - b. Self-reported measures [forget, miss30, miss7] in addition to the objective pill counts.
- 4) **Health-related quality of life:** Mean change from baseline in health-related quality of life

using PROMIS Global Health instrument [global01—global10]. There are two domains within this construct:

- a. Global Mental Health (assessed via a T-score)
- b. Global Physical Health (assessed via a T-score)

Safety Outcomes

We plan to evaluate the following safety outcomes:

- 1) Proportion of participants with *any* SAE according to the Good Clinical Practice (GCP) definition [sae_present, saedeath, saelifethrt, saehosp, saedisp, saecong, saeimpevnt].

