3. DEMOGRAPHICS AND BASELINE ASSESSMENTS

The following are specific demographic / baseline assessments of interest for analyses. Primary analyses will adjust for these covariates as we anticipate they will influence outcome. We plan to report both model-adjusted and simple unadjusted intervention effect estimates. In the cases of adjusted models, we will include the following variables as fixed effects, regardless of significance:

- 1) Sex [sex].
- 2) Age [age].
- 3) Race/ethnicity [ethnic]. We plan to categorize participants into White (ethnic = 1), Hispanic (ethnic = 3, 4, 5, 6), African American (ethnic = 2), or other categories. In the event of low cell counts in any one category, we may consider collapsing categories, foregoing adjustment for race (if collapsing cannot be justified scientifically), or failing to adjust for race altogether. We may also consider another potential covariate that is heavily related to race and ethnicity or conduct sensitivity analyses under different parameterizations / assumptions.
- 4) Literacy score according to the Newest Vital Sign (NVS, sum of [vs_totcal, vs_carb, vs_fat, vs_daily, vs_safe, vs_peanut]) as defined per scoring manual. The score ranges from 0-6, with 0-1 indicating limited literacy, 2-3 indicating likely limited literacy, and 4-6 indicating adequate literacy.
- 5) Indicator of monotherapy at baseline [inc04 = 3].

Additional demographics in general include:

- 1) Country of birth [birth].
- 2) Insurance status [insurance].
- 3) Education [edu].
- 4) Employment status [emplst].
- 5) Income [income_usd].
- 6) Marital status [marst].
- 7) Number of people in household [pple].

Note that some additional exploratory analyses may examine these additional demographic variables as covariates and/or effect modifiers as well. We will label any exploratory analyses involving additional potential covariates as post hoc in any dissemination materials.

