We will use simple sample Pearson correlation coefficients (and 95% confidence limits), Bland-Altman plots, or both to examine agreement among continuous outcome measures (primarily focused on office SBP and 24-hour SBP measures). Though these analyses are not the primary focus of this trial and its results, we will use agreement analyses to make inference regarding quality of SBP measurement methods and variability.

Analyses Contingent on Add-on Therapy Requirements

If there is evidence of a difference in proportion of participants requiring amlodipine add-on therapy at six weeks across arms, then we will also explore dividing the sample into four strata: (1) those that required amlodipine add-on treatment + received active control, (2) those that required add-on + received LDQT, (3) those that did not require add-on + received active control, and (4) those that did not require add-on and received LDQT. Depending on cell counts, we will attempt a series of exploratory analyses for key outcomes (SBP, DBP) to evaluate an effect. Additional analyses of this nature will be indicated as exploratory.

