8. POWER AND SAMPLE SIZE CONSIDERATIONS

The initial sample size calculations called for a total of 365 participants to be randomized (1:1 allocation). We anticipated an analytic sample size of 292 based on 365 participants at randomization and a 20% dropout rate by the 12-week follow-up time point. We originally based sample size and power calculations conservatively on an independent two-sample t-test. Based on results of interim analyses (refer to Section 10 for details), we updated our recruitment target to 87 participants (1:1 allocation). The analytic sample size of 77 is anticipated based on 87 participants at randomization.

and a conservatively estimated 12% dropout rate by the 12-week follow-up time point based on 8% dropout rate observed through September 2021.

The initial, conservative plan for primary outcome analyses involving an independent two-sample t-test provided an estimated 80% power to detect a 5 mmHg difference in SBP between the intervention and comparator arms assuming a two-sided 5% level of significance and a 15 mmHg standard deviation in outcome. This estimate is based on a 2017 Cochrane systematic review update evaluating the effects of fixed-dose combination therapy and systematic review on quarter dose combination therapy, and a pilot trial of quarter-dose combination therapy [3]. We assumed baseline SBP has a moderate correlation with follow-up SBP ($r \approx 0.50-0.6$); under this assumption, sample size calculations based on ANCOVA has the potential to allow for over 90% power under the same assumptions for remaining parameters.

At the request of the DSMB, we conducted an interim conditional power analysis, taking into consideration information from both the QUARTET USA trial data as of August 2021 and further the QUARTET (Australia) results.¹⁰ These interim analyses, incorporating information to date, suggested that a recruited sample size of at least 77, and a 12% dropout rate, would provide over 90% conditional power based on a sample of 87 randomized participants.

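### Significance pre-tests on visit-by-arm and visit decide what the primary 12-week SBP test is, and one branch names no model

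*SAP*

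**What the plan says.** The time point is fixed. Protocol 3.1 and SAP section 2 define the primary outcome as baseline-adjusted change in automated office SBP at 12 weeks, and SAP section 6 adds: "The primary study analysis time point for all relevant outcomes is 12 weeks post randomization".

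The analysis is a linear mixed model on week-6 and week-12 SBP, with arm, baseline SBP, visit, visit-by-arm and a random participant effect. SAP section 6 and Protocol 16.2 then reduce it in steps:

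1. If visit-by-arm "is insignificant at the 5% level, we will remove that term from the model".
2. Visit is tested next. No level is given at that point, but the general two-sided 5% rule of SAP section 6 covers it. If visit is dropped too, the primary hypothesis test is β1 = 0.
3. Otherwise, "if the visit-by-study arm interaction term or the visit term alone is significant, we will plan to evaluate the 12-week contrast" from least-squares means, and that is the primary analysis.

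The section also promises: "All between-arm differences at both six- and 12-week time points will be reported as model-based estimates". The six-week counterpart is secondary outcome 2a: "Mean change (from baseline) in automated office SBP [sbpavg] at six weeks".

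No model is named for the contrast in step 3 when only visit is significant. The SAP repeats the Protocol's sentence that leaves the details to the SAP, so nothing else fills the gap.

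**The concern.** There are two linked problems.

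First, a pre-test chooses the estimand. Once visit-by-arm is removed, β1 is a common effect over weeks 6 and 12 and no longer the week-12 effect named as primary. The interaction test making that choice has little power at 77 analysed.

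Second, the visit-only branch can be read in two ways. Taken in sequence, the interaction has already gone, so the 12-week contrast equals the pooled β1 and the primary result and secondary outcome 2a are the same number. If the interaction is meant to return, as the promise of differences at both visits suggests, the contrast is a true week-12 difference.

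Equal effects at the two visits cannot be taken for granted. Protocol section 4 starts open-label amlodipine at week 6 in participants whose blood pressure is uncontrolled, and SAP section 6 foresees unequal use by planning extra analyses "If there is evidence of a difference in proportion of participants requiring amlodipine add-on therapy at six weeks across arms". At stake is whether the primary p-value is settled before database lock.

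**Working it through.** **The plan's own figure.** 365 × 0.80 = 292 analysed, 146 per arm. SE = 15 × √(2/146) = 1.76; 5/1.76 = 2.85; power = Φ(2.85 − 1.96) = 81%, against the stated 80%. The current target also reproduces: 87 × 0.88 = 76.6, or 77. The conditional power cannot be checked, because the interim data are not given.

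**What the reduced model estimates.** With complete data, removing visit-by-arm makes β1 = (week-6 difference + week-12 difference)/2, whether or not visit stays in. In one simulated data set the full model gave −6.66 at week 6 and +1.44 at week 12. Both reduced models gave −2.61 = (−6.66 + 1.44)/2.

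**Inputs for size**
- SD: the Australian interval of 4.9–8.9 (Protocol 2.3) gives SE = 4.0/(2 × 1.96) = 1.02. Arms of 300 and 291 follow from 93/0.310 and 74/0.254. SD = 1.02/√(1/300 + 1/291) = 12.4. SAP section 8 (SD 15, baseline correlation r = 0.5–0.6) gives 15 × √(1 − r²) = 12.0–13.0.
- 77 analysed (39 vs 38); week-12 effect 6.9 mmHg from the Australian trial.
- Assumed, not in the documents: between-visit correlation ρ = 0.3–0.7, the share stepped up at week 6, and the arm difference in that share. Each share times 6–9 mmHg per drug (Protocol 2.1) gives the mean fall between visits and the gap between week-6 and week-12 effects.

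**Standard errors, for ρ = 0.3 to 0.7**
- Week-12 contrast: 12.4 × √(1/39 + 1/38) = 2.83.
- Pooled effect: 2.83 × √((1 + ρ)/2) = 2.28 to 2.61.
- Visit-by-arm: 2.83 × √(2(1 − ρ)) = 3.35 to 2.19. A true gap of 1.8 mmHg is 0.54–0.82 SE and is detected in 8–13% of trials.
- Visit: 12.4 × √(2(1 − ρ)/77) = 1.67 to 1.09. A 3.0 mmHg fall is 1.8–2.7 SE.

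So the visit test often succeeds where the interaction test fails, which is exactly the branch without a model.

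**Simulation.** 100,000 trials per scenario. Literal means the full-model week-12 contrast is used only if the interaction is significant; restored means it is used if the interaction or visit is significant. The week-6 effect is the larger one. Ranges are over ρ.

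| Case: share, arm difference, mmHg per drug | Fall / gap (mmHg) | Visit-only branch entered | p<0.05 verdict differs | Literal bias; coverage | Restored bias; coverage |
|---|---|---|---|---|---|
| A: 25%, 10 points, 6 | 1.5 / 0.6 | 13–26% | 3% | 0.2; 93.9–94.5% | 0.15–0.2; 94.1–94.6% |
| B: 50%, 20 points, 6 | 3.0 / 1.2 | 40–71% | 8–9% | 0.4; 93.2–94.1% | 0.1–0.3; 94.0–94.8% |
| C: 33%, 20 points, 9 | 3.0 / 1.8 | 39–67% | 8–9% | 0.6; 92.3–93.5% | 0.15–0.4; 93.6–94.7% |
| D: 50%, 20 points, 9 | 4.5 / 1.8 | 69–86% | 12–15% | 0.6; 92.3–93.5% | 0–0.2; 94.4–95.0% |
| E: 80%, 20 points, 9 | 7.2 / 1.8 | 87–91% | 12–20% | 0.6; 92.3–93.5% | about 0; 95% |

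- In the visit-only branch the two estimates differ by 0.8–1.3 mmHg on average.
- Constant 6.9 mmHg effect: verdicts differ in 8% of trials at a 3.0 fall and 10–14% at 4.5.
- Larger effect at week 12 (5.1, then 6.9): literal bias is −0.6.
- No effect at either visit: type I error is 5.3–6.0% literal; restored, 5.1–5.6% at a 3.0 fall and 5.0–5.2% at 4.5 or more.
- Stress case, 5 mmHg at week 6 and none at week 12: the literal reading rejects in about 9–15% of trials.
- The fixed full-model week-12 contrast holds about 5% type I error and 95% coverage throughout.

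**Check with missing data.** REML fits with 87 randomised, 12% of week-12 values missing completely at random, seven further covariate degrees of freedom and effects of 8.7 then 6.9 gave literal bias of 0.6–0.7 and coverage of 92–94%. Verdicts differed in 10% of trials at a 3.0 fall and 14–17% at 4.5.

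**The case against.** The rule is deterministic except in one branch, where one clause is missing. The restored reading is also the more natural one: a 12-week contrast, and differences at both visits, mean something only if visit-by-arm is in the model. On that reading bias is 0–0.4 mmHg and null type I error at most 5.6%.

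The disagreement rates depend on the scenario. With no fall in SBP they are at most 1%. With no treatment effect and a 3.0 mmHg fall they are about 2%. With a constant effect both readings are unbiased, and the disagreement reflects precision alone. The top of the range needs 80% stepped up, and no step-up share is documented; without that case the range is 8–15%. The Australian difference was sustained to 12 months (6.9, then 7.7 mmHg), which does not suggest shrinkage, although that is not a week-6 to week-12 comparison.

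All of this stands as a limit on size. It does not settle which p-value is primary. The more natural reading is still not written down, and even with the interaction restored, a pooled effect is tested whenever both pre-tests fail.

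**Conclusion.** The concern holds and should be fixed. That pre-tests select the primary test, and that the visit-only branch has no stated model, is certain from the text. The sizes are illustrative: they rest on SD 12.4, complete data, and assumed correlations, falls and gaps. The documents give no week-6 effect, so even the direction of any bias is unknown.

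Within those limits, the bias and the error inflation under a full null are modest. The main defect is that the same locked data can support two primary results, with different significance verdicts in roughly one trial in twelve to one in five once SBP falls materially between visits and the drug effect is real.

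**What to change.** In SAP section 6 and Protocol 16.2, delete the significance-based removal of terms. Always keep arm, visit, visit-by-arm and baseline SBP, and name the week-12 least-squares-mean contrast from that model as the single primary test. Take the six-week secondary contrast from the same model, and report the interaction test and pooled effect as supportive. Alternatively, pre-specify the pooled effect as primary and relabel the endpoint.

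Also state whether the primary version includes sex, age, race/ethnicity, literacy and baseline monotherapy. SAP section 3 says "Primary analyses will adjust for these covariates as we anticipate they will influence outcome", while section 6 plans both adjusted and unadjusted analyses.

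The cost is wording in two documents and some power:

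| Constant effect | Fixed week-12 contrast | Literal | Restored, fall 3.0 | Restored, fall 4.5 |
|---|---|---|---|---|
| 6.9 mmHg | 68% | 74–83% | 69–77% | 68–72% |
| 5 mmHg | 42% | 47–58% | 43–51% | 42–46% |

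SAP section 8 says the revised target "would provide over 90% conditional power based on a sample of 87 randomized participants" without naming the test. That figure should be restated for the chosen test. It uses interim data, so it cannot be set directly against the unconditional powers above. A sponsor who wants the extra power can take the pooled option, provided it is declared before database lock.
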